#### Rationale

As of March 20, 2020, the novel 2019-coronavirus has infected nearly 250,000 people resulting in over 10,000 deaths. There is no known treatment for this disease. Among the subset of patients who develop critical illness, evidence points towards the development of a cytokine storm syndrome that is similar to what is observed in secondary hemophagocytic lymphhistiocytosis (sHLH). Clinical and laboratory features of sHLH include high fevers, elevated ferritin, elevated triglycerides, low fibrinogen, and cytopenias. About half of the patients with sHLH develop ARDS which carries a high mortality (1). In China, hypercytokinemia was observed in patients with severe COVID disease and one study published online associated elevations in ferritin and IL-6 with greater mortality risk in these patients (6). It is reasonable to postulate that the pulmonary involvement may be the result of unchecked hyperinflammation, and that there may be a benefit to immunosuppressive, specifically, anti-cytokine therapies. Currently a multicenter randomized trial to evaluate the IL-6 receptor blocker tocilizumab is rolling out in China. Vitaeris Inc manufactures a direct IL 6 inhibitor, clazakizumab, which is currently under phase 3 investigations for patients with chronic active antibody mediated rejection after kidney transplantation. Recognizing, based on its mechanism of action, clazakizumab is hypothesized to have benefit for patients with life-threatening COVID-disease, Vitaeris is willing to provide drug for this investigator initiated trial for use in patients who are at greatest risk of dying from COVID-19 disease. This study is a prospective, randomized, double-blind, placebo-controlled trial of clazakizumab to prevent death from respiratory and multi-organ failure in COVID-19 disease. An under recognized comorbidity in SARS-CoV-2 infected patients is acute kidney injury (AKI) occurring in up to 30% of critically ill patients, and contributing to fluid retention, worsening oxygenation, and the need for renal replacement therapy (RRT). While multiple etiologies may be at play, the effects of systemic and possibly local inflammation are highly likely to be significant contributing factors. Improving renal function via IL-6 inhibition would be a substantial clinical benefit.

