## **Study Design and Endpoints**

This is a randomized, double-blind, placebo-controlled, design. We propose the administration of an investigational drug in patients with high predicted short-term mortality secondary to COVID-19 disease. 30 Patients will be randomly assigned in a 1:1 ratio to two study arms that will receive clazakizumab at a dose of 25 mg or placebo.

Primary Study Endpoints

The primary endpoint is patient safety assessed by serious adverse events associated with clazakizumab or placebo.

Secondary Study Endpoints

The secondary endpoints are: incidence of intubation, time to extubation, length of ICU stay, trend in C-reactive protein, severity of AKI, need for RRT, duration of RRT, and patient survival at 28 and 60 days.

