# Eligibility

# Inclusion Criteria

In order to be eligible to participate in this study, the patients must meet all of the following criteria:

- At least 18 years of age
- Confirmed COVID-19 disease (by Cobas SARS-CoV-2 real time reverse transcription polymerase chain reaction (RT-PCR) using nasopharyngeal swab sample, or equivalent test available to be performed by the Columbia University Irving Medical Center (CUIMC)/New York Presbyterian (NYP) clinical laboratory). Effort will be made to have the confirmatory test result <72 hours prior to enrollment however given overall clinical demand this may not be feasible in all cases.
- Respiratory failure manifesting as: Acute Respiratory Distress Syndrome (defined by a P/F ratio of <200), OR oxygen saturation (SpO2) < 90% on 4 liters (L) (actual or expected given higher O2 requirement) OR increasing O2 requirements over 24 hours, plus 2 or more of the following predictors for severe disease:

- CRP > 35 mg/L Ferritin > 500 ng/mL D-dimer > 1 mcg/L Neutrophil-Lymphocyte Ratio > 4 Lactate dehydrogenase (LDH) > 200 U/L Increase in troponin in patient w/out known cardiac disease
- Has a consent designee willing to provide informed consent on behalf of the patient (this
  assumes that a mechanically ventilated patients lacks capacity to consent on his/her own behalf.
  Should it be deemed that the patient has capacity to consent, consent may be obtained from
  the patient.)
- Women of childbearing potential must be willing and able to use at least one highly effective contraceptive method for a period of 5 months following the study drug administration. In the context of this study, an effective method is defined as those which result in low failure rate (i.e. less than 1% per year) when used consistently and correctly such as:
  - combined (estrogen and progestogen containing) hormonal contraception combined (estrogen and progestogen containing) hormonal contraception (oral, intravaginal, or transdermal)
  - progestogen-only hormonal contraception associated with inhibition of ovulation (oral, injectable, implantable)
  - intrauterine device (IUD)
  - intrauterine hormone-releasing system (IUS)
  - vasectomized partner
  - o bilateral tubal occlusion
  - true abstinence. when this is in line with the preferred and usual lifestyle of the subject.
     Periodic abstinence, such as calendar, ovulation, symptothermal, postovulation methods, and withdrawal are not acceptable methods of contraception.

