## **Strategies for Recruitment and Retention**

The patients enrolled will be identified by the members of the Columbia University Irving Medical Center / New York Presbyterian Hospital (CUIMC/NYPH) COVID-19 inpatient team who have identified the potential subject as critically ill and failing all available medical and supportive therapies. Patient recruitment will begin by direct communication between the COVID-19 inpatient team and the study team. An individual involved in the patient's care must determine and document that the patient or their surrogate (if the patient lacks capacity) has agreed to discuss the study with the researchers. Duration of Study Participation

The entire duration of study participation is 60 days. Study specific laboratory tests will be performed within the first 14 days of study initiation. Beyond 14 days, all data collected will be that which is acquired for purposes of clinical care. Patients will be followed for the survival endpoint for 60 days. Total Number of Participants and Sites

The CUIMC/NYP inpatient hospital site is expected to enroll up to30 patients across the 2 arms. NYU will serve as the central data managing site, and will analyze data from patients enrolled at NYU, Columbia, and Johns Hopkins. Total enrollment is expected to be 150 patients across three sites. Expected contribution of patients will be: NYU Langone (New York, NY): 90 total patients (80 already randomized 1:1:1 and 10 to be randomized 1:1 for high-dose clazakizumab 25mg vs placebo) Johns Hopkins Medicine (Baltimore, MD): 30 patients to be randomized 1:1 for high-dose clazakizumab 25mg vs placebo New York-Presbyterian/Columbia University (New York, NY): 30 patients to be randomized 1:1 for high dose clazakizumab 25mg vs placebo Columbia and Johns Hopkins will contribute de-identified data to the central dataset but the conduct of the trial at each site will be overseen by the local IRB the respective sites.

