## Participant Withdrawal or Termination

The predicted mortality rate for patients with COVID-19 and ARDS is in excess of 50% (7). As such we anticipate there will be mortality amongst some of the participants. Death will constitute withdrawal from the trial. Otherwise we would not anticipate premature withdrawal from the study as the patients are expected to remain hospitalized (likely in an ICU setting) for the entire duration of the 14-day period where study specific data are collected. If the patient is discharged before day 28 survival status will be obtained by patient lookup in the electronic medical record. For discharged patients in whom there is no definitive record documenting patient status (alive or dead) after 28 days have elapsed, the study team will contact the patient or patient's family by phone to assess patient survival and to assess for the occurrence of any interim AEs/SAEs. At end of study (day 60), a phone call will also take place to assess patient survival and again asses for interim AEs/SAEs. The IP administration will occur over a maximum of 3 days following enrollment. Study specific laboratory tests will be performed in the first two weeks and if a patient (or consent designee should the patient lack capacity) wishes to withdraw from participation and refuse these laboratory studies, they will be free to do so.

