## Statistical and Analytical Plans (SAP)

Descriptive statistics for the safety endpoints will be used. With 10 patients, the 95% confidence interval (CI) around the rate of SAEs will be no more than 0.62 units wide. With 20 patients (combining the low dose and high-dose groups), the 95% CI will be no more than 0.46 units wide. Regarding the secondary outcome of patient survival, too little is known about the expected clinical behavior of these patients to make meaningful projections about expected changes in mortality given drug efficacy. Data will be analyzed across three sites: NYU, where this protocol originated; Columbia/NYP; and Johns Hopkins.

The first 80 patients at NYU were enrolled in the three-arm study using a 1:1:1 ratio. Following the DSMB's recommendation, additional NYU patients (expected to be 10) will be randomized in a 1:1 ratio to placebo or 25 mg clazakizumab. Columbia/NYP and Johns Hopkins will each enroll 30 patients in a 1:1 randomization ratio, with 15 patients each on clazakizumab 25mg and placebo. At these other sites, with 15 patients, the 95% confidence interval (CI) around the rate of SAEs will be no more than 0.52 units wide. The total planned enrollment of 150 subjects across these three sites will considerably increase the power to detect treatment effects. The table below summarizes approximate power for the projected sample size in the placebo and 25 mg clazakizumab groups (N=60 in each arm) to detect various reductions in mortality from the expected 50% rate in the placebo group, for various levels of Type I error (alpha) assuming use of a two-sided test. For example, we have approximately 82% power

to detect a reduction in the mortality rate of 50%, from 0.5 in the placebo group to 0.25 in the treated group, assuming 60 patients per group, at the usual Type I error rate of 0.05.

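### Is the 82% mortality power undermined because the SAP does not say whether its 50% placebo rate refers to day 28 or day 60?

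*Combined protocol and SAP*

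**What the plan says.** The Statistical and Analytical Plans section gives approximate power for the placebo and 25 mg groups, 60 patients in each, against "various reductions in mortality from the expected 50% rate in the placebo group". The power table that it introduces is described as being "for various levels of Type I error (alpha) assuming use of a two-sided test". Its worked example is a fall "from 0.5 in the placebo group to 0.25 in the treated group", with about 82% power at a Type I error of 0.05, which it calls the usual rate. Earlier in the same section it says that too little is known about these patients for meaningful projections of mortality change.

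Four other places bear on the point:

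- Study Design and Endpoints makes serious adverse events the primary endpoint and lists "patient survival at 28 and 60 days" among the secondary endpoints.
- Strategies for Recruitment and Retention says "Patients will be followed for the survival endpoint for 60 days".
- Participant Withdrawal or Termination gives the only referenced mortality figure: "The predicted mortality rate for patients with COVID-19 and ARDS is in excess of 50% (7", where the 7 is the reference number. The reference list shows a series of 21 critically ill patients.
- The Inclusion Criteria admit patients by ARDS, by low oxygen saturation, "OR increasing O2 requirements over 24 hours, plus 2 or more of the following predictors for severe disease".

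**The concern.** A mortality rate has meaning only with a time attached. Deaths accumulate, so one 50% placebo rate can hold at both day 28 and day 60 only if no placebo patient dies in between. The SAP text does not say which day it means, does not cite the rate where it is used, and gives power at several alpha levels. The one referenced figure carries no day either, and it describes ARDS, which is only one of three respiratory routes into the trial.

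If the true rate were lower than 50%, power for the same relative reduction would fall. If no day is named, an analyst could in principle emphasise whichever day looked better. That would matter in what the Rationale calls a "trial of clazakizumab to prevent death from respiratory and multi-organ failure in COVID-19 disease", where mortality is the only efficacy outcome with a power statement.

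**Working it through.** **Inputs.** From the SAP: placebo rate p1 = 0.50, treated rate p2 = 0.25, n = 60 per arm, two-sided alpha 0.05 (z = 1.96).

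**1. Reproduce the plan's figure.** Two-proportion test with pooled variance under the null:

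Power = Φ{[(p1 − p2) − 1.96 × SE0] / SE1}, with SE0 = √[2p̄(1 − p̄)/n] and SE1 = √{[p1(1 − p1) + p2(1 − p2)]/n}.

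- p̄ = 0.375, so SE0 = √(2 × 0.375 × 0.625/60) = 0.0884.
- SE1 = √[(0.25 + 0.1875)/60] = 0.0854.
- Power = Φ[(0.25 − 1.96 × 0.0884)/0.0854] = Φ(0.899) = 81.6%.

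The stated 82% is correct.

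**2. Sensitivity to the placebo rate.** Same formula, mortality halved, 60 per arm. Every rate except 50% is an assumption; the documents give no day-specific rate.

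| Placebo rate | Treated rate | Power |
|---|---|---|
| 30% | 15% | 50% |
| 40% | 20% | 67% |
| 45% | 22.5% | 75% |
| 50% | 25% | 82% |
| 55% | 27.5% | 87% |
| 60% | 30% | 92% |

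Power reaches 80% at a placebo rate of 48.8%. If the 25-point absolute difference is held instead of the halving, a lower placebo rate raises power: 84% for 45% versus 20%, and 88% for 40% versus 15%.

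**3. What the missing day does.** If 50% is the day-60 rate, the day-28 rate is at most 50%, and day-28 power for a halving is at most 82% (67% to 75% if the day-28 rate is 40% to 45%). If 50% is the day-28 rate, the day-60 rate is at least 50%, and day-60 power for a halving is at least 82%. The direction depends on a reading that the text leaves open, and the only referenced figure is above 50%.

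**4. Testing both days.** Suppose each day were tested at 0.05 and either result counted as decisive. Day-28 deaths are a subset of day-60 deaths, so with p28 and p60 the mortality rates by days 28 and 60, the two test statistics correlate at √{p28(1 − p60)/[p60(1 − p28)]}. With an assumed day-60 rate of 50% and day-28 rates of 45%, 40% and 30%, the correlations are 0.905, 0.816 and 0.655. The bivariate normal chance of at least one false positive is then 7.0%, 7.7% and 8.5%. No section of the plan describes that procedure.

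**5. Splitting alpha.** One test of 50% versus 25% at alpha 0.025 has 73% power. That is not the power of a two-day procedure. Simulation (400,000 trials, 60 per arm, mortality halved, 0.025 per day) gives the chance of at least one significant day as 76% for placebo rates of 40% or 45% at day 28 and 50% at day 60. It gives 82% for 50% and 55%, and 88% for 50% and 60%.

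**The case for a change.** The best case for a change is this. The mortality power cannot be tied to a defined comparison. The margin is thin, since 80% power needs a placebo rate of at least 48.8%. The support for 50% is a 21-patient series cited for ARDS, while eligibility is wider. Naming a day, a test and an alpha before unblinding would cost a few sentences and no patients.

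Some of this stands. The SAP text names no day, the rate is uncited where it is used, and the cited figure describes only part of the eligible population.

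The rest carries less weight. The rate does have a source within the document, although the SAP does not point to it. A range that looks only below 50% is one-sided when the only referenced figure lies above it. The 7.0% to 8.5% false-positive chance belongs to a pair of decisive tests that the plan does not state. Date of death is collected and follow-up for survival runs to 60 days, so a single time-to-event comparison fits the text equally well. On alpha, the SAP's worked example uses 0.05 and calls that level the usual one.

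**Conclusion.** The concern does not call for a change. What remains is a missing detail: the SAP text does not say which day its 50% and 82% refer to, and it does not point to the cited figure in the withdrawal section. No number is wrong, and none of the plan's rules is shown to fail.

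Three features keep the consequence small. Mortality is a secondary endpoint in a trial with safety as its primary endpoint. The power was worked out for a sample size already projected from the three sites' contributions, so another planning rate would change the table but not the enrolment. Survival status is scheduled at both days, so results at each can be reported soundly whichever day the planner had in mind. A reader can meanwhile take the 82% as the power at whichever day placebo mortality is 50%, which is how an illustrative calculation is normally read.

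In size, a placebo rate ten points lower or higher moves power for a halving from 82% to 67% or 92%. Those alternatives are assumptions, and the documents do not show that 50% is too high or too low. The conclusion also allows for the power table, which was not available in the text reviewed: its title or footnote may already name the day.
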